5.3.2 PAC-1

In Phase 1b, PAC-1 (PO) will be dosed at 625 or 750 mg daily in the morning on Days 1-21 of each 28 day cycle (for exception in cycle 1, see below). The dose which is determined to be the MTD will be taken in the morning on Days 1-21 of the cycle in Phase 2.

During Cycle 1 for each dose level, subjects will be instructed to administer their daily dose at the same approximate time (+/- 1 hour) each morning. Subsequent cycles must meet the criteria found in section 6.1. The study drug will be administered in the morning and on an empty stomach with the patient remaining NPO (nothing by mouth), except for water and prescribed medications, for 2 hours before and 1 hour after each dose. Patients will be instructed to take each oral dose of PAC-1 with 8 ounces of water (1 cup, 240 mL).

For Cycle 1, PAC-1 will be given on Day 1 and withheld on Days 2 and 3. The dose on these days are being held in order to determine the PK of single-agent entrectinib on Day 3 of the cycle. PAC-1 treatment will be re-initiated on Day 4 and continue to Day 21 of the 28-day cycle. Administration of PAC-1 on Days 1 and 21 of Cycle 1 will occur in the morning. Information on the time and number of PAC-1 doses received for the 96 hours prior to the dose on Day 21 will be obtained from subjects.

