2.3 Correlative/Exploratory Objectives

- Determine pharmacokinetics (PK)/pharmacodynamics (PD) of PAC-1 alone after single dosing and after repeated dosing and in combination with entrectinib (Phase 1b only).
- Determine pharmacokinetics/pharmacodynamics of entrectinib alone after single dosing and after repeated dosing and in combination with PAC-1 (Phase 1b only).
- Compare procaspase 3 expression in tumor tissue to degree of clinical response
- Determine correlation between CTC number and clinical response.

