5.2 Phase 2 Study

At the completion of the phase 1b study, the safety of the PAC-1 and entrectinib combination will be assessed and recommendations will be provided regarding whether to proceed to the phase 2 portion of the study. The sponsor-investigator, Vanquish Oncology, and Genentech will review the DSMB recommendations, and make a decision regarding whether this combination is safe to warrant further study of this combination in a phase 2 study.

The primary objective of the Phase II trial is to determine the activity of the combination of PAC-1 and entrectinib for subjects with uveal melanoma as assessed by PFS at 3 months. Entrectinib, 600 mg orally, will be given Days 1 to Day 28 of each cycle and the recommended phase 2 dose (RP2D) of PAC-1 (PO) will be given on Days 1 to Day 21. Each cycle is 28 days. Treatment will continue until disease progression (based on RECIST 1.1 criteria), unacceptable toxicity, subject withdrawal of informed consent, or subject death either from progression of disease, the therapy itself, or from other causes. Subjects who voluntarily withdrew from study treatment, have progressive disease, or unacceptable toxicities will be followed for survival every 2 months for 12 months from start of study treatment, then every 3 months for up to 24 months.

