5.3.1 Entrectinib

Entrectinib (PO) will be dosed at 600 mg daily in the evening on Days 1-28 of each 28 day cycle (for exception in Cycle 1, see below). During Cycle 1 for each dose cohort, subjects will be instructed to administer their daily dose at the same approximate time (+/- 1 hour) each evening. The study drug will be administered in the evening. Patients will be instructed to take each oral dose of entrectinib with 8 ounces of water (1 cup, 240 mL) and with food.

Entrectinib therapy will be withheld on Days 1 and 2 and initiated during Cycle 1 on Day 3 to continue for the remainder of the cycle. Administration of entrectinib on Days 3 and 21 of Cycle 1 will occur in the morning. Entrectinib administration will occur 1 hour before PAC-1 on Day 21. Information on the time and number of entrectinib doses received for the 96 hours prior to the dose on Day 21 will be obtained from subjects.

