7: Cycle = 28 days. PAC-1 will be taken once daily, Days 1-21. For Cycle 1, PAC-1 will be given on Day 1 and withheld on Days 2 and 3. The dose on these days is being held in order to determine the PK of single-agent entrectinib on Day 3 of the cycle. PAC-1 treatment will be re-

initiated on Day 4 and continue until Day 21 of the 28 day cycle. Administration of PAC-1 on Days 1 and 21 of Cycle 1 will occur in the morning. Entrectinib will be taken once daily, Days 1-28. Entrectinib therapy will be withheld on Days 1 and 2 and initiated during Cycle 1 on Day 3 to continue until Day 28 of the 28 day cycle. Administration of entrectinib on Days 3 and 21 of Cycle 1 will occur in the morning. Entrectinib administration will occur 1 hour before PAC-1 on Day 21.

8: The PK and PD analyses will occur with each dose level during Phase Ib. Pharmacokinetic and pharmacodynamic sample collections will occur in the mornings on Day 1(PAC-1 only), Day 3 (entrectinib only), and Day 21 (PAC-1 and entrectinib) of the first cycle. Day 1 Cycle 1: Subjects receive only PAC-1. Blood samples are collected immediately prior to oral ingestion of PAC-1 and at the following time points after ingestion: 0.5, 1, 2, 3, 4, 6, 7, and 24 hours. Day 3 Cycle 1: Subjects receive only entrectinib. Blood samples are collected immediately prior to oral ingestion of entrectinib and at the following time points after ingestion: 0.5, 1, 2, 3, 4, 6, 7, and 24 hours. Day 21 Cycle 1: Subjects receive both PAC-1 and entrectinib. Entrectinib will be taken 1 hour before PAC-1. Blood samples are collected immediately prior to oral ingestion of entrectinib, 0.5 hour before ingestion of PAC-1, and at the following time points after ingestion of PAC-1: 0.5, 1, 2, 3, 4, 6, 7, and 24 hours. See Correlative Laboratory Manual (CLM) for additional details regarding these samples.

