8.1 Peripheral Blood Samples

8.1.1 Plasma for Pharmacokinetics and Pharmacodynamics

In phase 1b, the pharmacokinetics (PK) and pharmacodynamics (PD) of PAC-1 will be assessed following doses administered on Days 1 and 21 of the first cycle. In phase 1b, the PK and PD of entrectinib will be assessed following the dose administered on Days 3 and 21 of the first cycle. Entrectinib will be withheld on Days 1 and 2 to allow assessment of PAC-1 PK when administered as single agent. PAC-1 will be withheld on Days 2 and 3 to allow assessment of entrectinib PK when administered as single agent on Day 3. PKs of both drugs will be assessed on Day 21 to determine effects of repeated dosing or combining of the two drugs. The PK and PD analyses will occur with each dose level.

Administration of PAC-1 on Days 1 and 21 and entrectinib on Days 3 and 21 of Cycle 1 will occur in the morning. Entrectinib administration will occur 1 hour before PAC-1 on Day 21. The dose timing on this day is being specified to accommodate a sampling schedule that minimizes the number of blood draws needed from the patient. Information on the time and number of PAC-1 and entrectinib doses received for the 96 hours prior to the dose on Day 21 will be obtained from subjects. Patients will not receive their PAC-1 dose on Days 2 and 3 of Cycle 1. The doses on these days are being held in order to accurately define the absorption and metabolism of entrectinib when administered as a single agent on Day 3. Likewise, patients will not receive their entrectinib dose on Days 1 and 2 of Cycle 1. The doses on these days are being held in order to accurately define the absorption and metabolism of PAC-1 when administered as a single agent on Day 1. Actual and nominal sample collection times will be recorded on the case report forms and sample tubes.

Sample collections will occur in the mornings on Day 1 (PAC-1 only), Day 3 (entrectinib only), and Day 21 (PAC-1 and entrectinib) of the first cycle.

- Day 1, Cycle 1: Subjects receive only PAC-1.
 - Blood samples are collected immediately prior to oral ingestion of PAC-1 and at the following time points after ingestion: 0.5, 1, 2, 3, 4, 6, 7, and 24 hours.
- Day 3, Cycle 1: Subjects receive only entrectinib.
 - Blood samples are collected immediately prior to oral ingestion of entrectinib and at the following time points after ingestion: 0.5, 1, 2, 3, 4, 6, 7, and 24 hours.
- Day 21, Cycle 1: Subjects receive both PAC-1 and entrectinib.

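### Phase 1b, Cycle 1 Day 21: entrectinib with food is due 1 hour before PAC-1, inside the PAC-1 fast, so the dosing instructions cannot all be followed (minor; exploratory PK only)

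*Combined protocol and SAP*

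**What the plan says.** **PAC-1.** Section 5.3.2 has PAC-1 taken fasted in the morning, and the fasting rule reads: "remaining NPO (nothing by mouth), except for water and prescribed medications, for 2 hours before and 1 hour after each dose". In Cycle 1 the dose is to be taken at the "same approximate time (+/- 1 hour) each morning".

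**Entrectinib.** Section 5.3.1 makes it an evening drug: "Patients will be instructed to take each oral dose of entrectinib with 8 ounces of water (1 cup, 240 mL) and with food". Section 10.2.5 repeats the food requirement.

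**Day 21.** Section 5.3.1 moves the Cycle 1 Day 3 and Day 21 entrectinib doses to the morning and adds: "Entrectinib administration will occur 1 hour before PAC-1 on Day 21". Section 7 (footnotes 7 and 8) and Section 8.1.1 repeat the 1-hour gap. Section 8.1.1 explains it as a way to limit the number of blood draws and does not mention food.

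**Use of the data.** Section 8.1.1.1 compares PAC-1 exposure on Day 1 with Day 21, and entrectinib exposure on Day 3 with Day 21, through geometric mean ratios with 90% confidence intervals. Footnote 8 of Section 7 sets the scope: "The PK and PD analyses will occur with each dose level during Phase Ib". Section 2.3 likewise lists the combination PK as "in combination with PAC-1 (Phase 1b only").

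**The concern.** On ordinary days the morning and evening schedule keeps the fasted drug and the fed drug apart. Day 21 of Cycle 1 brings them together, and it is the only day on which the combination is sampled. A site reading Sections 5.3.1 and 5.3.2 together has to break one instruction, and different sites may break different ones.

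What is at stake is how the Day 21 comparisons can be read. A change in exposure between the single-agent day and Day 21 could partly reflect food. If every site resolves the conflict in the same way, the mismatch is systematic and more patients will not average it out. If sites differ, it adds variation between patients. The documents do not ask for food state to be recorded, so the analyst could not tell which had happened.

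**Working it through.** The plan states no figure to reproduce. The check is one of timing, with the PAC-1 dose at t = 0 hours.

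**Step 1: the conflict.**
- Fast (Section 5.3.2): t = -2 to t = +1.
- Entrectinib with food (Sections 5.3.1 and 10.2.5; timing also in Section 7 and Section 8.1.1): t = -1.
- Since -2 < -1 < +1, the food falls inside the fast. It comes -1 - (-2) = 1 hour after the fast begins.
- The exemption for prescribed medications covers the capsules but not the food.

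**Step 2: search for an exception.** The Cycle 1 exceptions in Sections 5.1, 5.3.1 and 5.3.2 cover held days, time of day and the order of dosing. Section 5.7 (Diet) does not address Day 21. Sections 8.1.1 and 8.1.1.1 give no meal rule.

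**Step 3: consequence for the two comparisons.** This assumes that Day 1 (PAC-1 fasted) and Day 3 (entrectinib fed) are taken as instructed.

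| Day 21 choice | PAC-1, Day 1 vs Day 21 | Entrectinib, Day 3 vs Day 21 |
|---|---|---|
| Full meal with entrectinib | mismatched | matched |
| Food withheld | matched | mismatched |
| Partial meal | possibly mismatched | possibly mismatched |

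With a 1-hour gap, no choice satisfies both food rules.

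**Step 4: reach.** Section 12.3.1 gives 9 to 12 Phase 1b patients. The number analysed will be lower if profiles are incomplete (Section 8.1.1.1), and it is zero if the analyses are not funded (Section 8).

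**Step 5: what a longer gap does to sampling.** The present Day 21 draws are one before entrectinib, one at t = -0.5, and eight at t = 0.5, 1, 2, 3, 4, 6, 7 and 24, so 1 + 1 + 8 = 10. Time after entrectinib equals t plus the gap.

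| Gap | Post-dose entrectinib times (h) | Count | First | Last | Entrectinib dose to 7-hour PAC-1 draw |
|---|---|---|---|---|---|
| 1 h (now) | 0.5, 1.5, 2, 3, 4, 5, 7, 8, 25 | 9 | 0.5 | 25 | 1 + 7 = 8 h |
| 2.5 h | 2, 3, 3.5, 4.5, 5.5, 6.5, 8.5, 9.5, 26.5 | 9 | 2 | 26.5 | 2.5 + 7 = 9.5 h |

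For comparison, Day 3 has eight post-dose samples at 0.5, 1, 2, 3, 4, 6, 7 and 24 hours, two of them within the first hour. The 2.5-hour gap assumes 30 minutes for the meal: 2.5 - 0.5 = 2 hours, which is when the fast starts. PAC-1 sampling does not change under either gap.

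**The case against.** **The laboratory manual may settle it.** The protocol sends readers there for sample details, and it cannot be checked here. This stands as a limit: the claim is that the protocol and SAP contain no Day 21 food rule, not that none exists anywhere. If the manual has one, the dosing text should still agree with it.

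**The comparisons are weak already.** This is true. They are exploratory, small and dependent on funding. They also mix repeated dosing with co-administration, and entrectinib moves from evening to morning that day. Correcting the food state would not separate those effects. This limits the importance of the point but does not remove the contradiction.

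**A longer gap has its own costs.** This also stands. Early entrectinib sampling becomes sparser, the last sample moves further from 24 hours, and the interval from the Day 20 evening dose shortens. Nor does clearing the fast guarantee identical PAC-1 conditions: Day 1 may follow a longer fast, while Day 21 follows a meal by about 2 hours. Naming the rule that yields is simpler and changes no clock times, but it leaves one comparison mismatched.

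**A stronger reading: Phase 2 patients are affected too.** The Day 21 sentence in Section 5.3.1 and footnote 7 of Section 7 carry no phase limit, so a reader might extend the conflict to the 29 additional Phase 2 patients. The documents do not support that. Section 5.1 places the Cycle 1 exceptions under the Phase 1b plan. Section 5.3.2 attaches its exception to a Phase 1b sentence. Section 8.1.1 ties the timing to PK sampling, which is Phase 1b only. Section 5.2 gives Phase 2 dosing without any exception: "Entrectinib, 600 mg orally, will be given Days 1 to Day 28 of each cycle". What remains is a missing label.

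**Conclusion.** The contradiction holds on the text: on Phase 1b Cycle 1 Day 21 the entrectinib food rule, the 1-hour gap and the PAC-1 fast cannot all be kept. If Days 1 and 3 follow instructions, at least one of the two Section 8.1.1.1 comparisons has mismatched food states in every patient sampled, out of 9 to 12 at most.

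Confidence is high for the contradiction and low for any effect on the results. The documents give no food effect for either drug, so size and direction are unknown and the effect could be nil. A reader might infer that the interaction estimates are biased or that dose selection is compromised. The documents support neither inference: the first needs a food effect they do not report, and the MTD and RP2D rest on DLTs in Cycle 1 and other toxicity, not on these PK comparisons. The Phase 2 endpoint is likewise unaffected.

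Severity is minor. The text is wrong as written, for exploratory PK only.

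**What to change.** **Preferred change.** Amend Section 5.3.1, Section 7 (footnotes 7 and 8) and Section 8.1.1 so that Phase 1b Cycle 1 Day 21 has one fixed nominal gap that clears the fast. An example is entrectinib with food 2.5 hours before PAC-1, the meal finished by 2 hours before. Keep the dosing order and the 10 draws, and leave PAC-1 at its usual time. Delaying PAC-1 by the full 1.5 hours (2.5 - 1) instead would exceed its 1-hour tolerance.

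**Downsides.** The first post-dose entrectinib sample moves from 0.5 to 2 hours and the last from 25 to 26.5 hours. The first draw and the entrectinib dose come 1.5 hours earlier, and the interval from the Day 20 evening dose shortens by the same amount. If an early sample matters, one added draw 0.5 hour after entrectinib restores it, at 11 draws and 10 mL more blood.

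**If the 1-hour gap is kept.** State which food rule yields on Day 21 and report the affected comparison as food-mismatched.

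**In either case.** Record food state and meal time for the Day 1, 3 and 21 PK doses, and add a sentence to Section 8.1.1.1 flagging patients whose food state differs between the days compared. Separately, as a clerical repair, add the Phase 1b label to the Cycle 1 holds and the Day 21 timing in Section 5.3.1 and footnote 7.

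**Cost.** The cost is a short wording amendment notified to the IRB (Section 15.1) and two form fields. If the gap changes, nominal times must be updated in the laboratory manual and wherever they are recorded, since Section 8.1.1 says: "Actual and nominal sample collection times will be recorded on the case report forms and sample tubes".

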5.4 Supportive Care

Optimal care should be given to all subjects. Subjects should receive full supportive care during the study, including transfusion of blood and blood products, treatment with antibiotics, analgesics, erythropoietin, or bisphosphonates, when appropriate. Although acetaminophen at doses of \leq 2 grams/day is permitted, it should be used with caution in subjects with impaired liver function.

Nausea/vomiting: Nausea and vomiting should be treated aggressively, and consideration should be given in subsequent cycles to the administration of prophylactic antiemetic therapy according to standard institutional practice. If prophylactic antiemetic therapy is needed, 5-HT3 receptor antagonists (without corticosteroids) should be tried first. Due to the potential of benzodiazepines to cause sedation, the use of benzodiazepines for antiemetic prophylaxis should be reserved for subjects who cannot be satisfactorily managed otherwise. Subjects should be strongly encouraged to maintain liberal oral fluid intake.

5.5 Concomitant Medications

Medications or vaccinations specifically prohibited in the exclusion criteria are not allowed during the ongoing trial. If there is a clinical indication for one of these or other medications or vaccinations specifically prohibited during the trial, discontinuation from trial therapy or vaccination may be required. The investigator should discuss any questions regarding this with the sponsor-investigator by contacting the HCRN Project Manager. The final decision on any supportive therapy or vaccination rests with the investigator and/or the subject's primary physician.

5.5.1 Permitted Concomitant Medications

Medications required to treat AEs, manage cancer symptoms, concurrent diseases and supportive care agents, such as pain medications, anti-emetics and anti-diarrheal medications are allowed. In

general, the use of any concomitant medication deemed necessary for the care of the subject is permitted in this study, except as specifically prohibited below.

The subject must be told to notify the investigational site about any new medications subject takes after the start of the study treatment. All medications (other than study drugs) and significant non-drug therapies (including vitamins, herbal medications, physical therapy and blood transfusions) administered within 30 days of study entry and during the study must be listed on the Concomitant medications/Significant non-drug therapies section of the subject record.

Although acetaminophen at doses of \leq 2 grams/day is permitted, it should be used with caution in subjects with impaired liver function.

5.6.2 Permitted Concomitant Therapy Requiring Caution

Entrectinib is mainly eliminated through hepatic clearance and CYP3A4 plays a significant role in the biotransformation of entrectinib. Co-administration of strong or moderate CYP3A4 inhibitors and inducers should be avoided. In vitro, entrectinib exhibited potential to inhibit and induce the activities of CYP3A, and potential for inhibition of CYP2C9 and CYP2D6, which suggests a potential for interaction with other drugs metabolized by these isoforms. Because of this, entrectinib should be administered with caution with the drugs listed in Appendix 2.

In addition, since absorption of entrectinib is pH sensitive, patients using H2-receptor antagonists, proton pump inhibitors (PPIs), and/or antacids should discontinue these drugs prior to starting entrectinib. If not possible, or if after discontinuation such therapy needs to be resumed, patients should be instructed to take only H2 receptor antagonists or antacids, if possible, as the duration of action of these drugs is relatively transient compared with PPIs that have longer half-lives, and thus may be administered at safe intervals in relation to entrectinib. These medications should be taken at a time point that is not proximal to entrectinib administration (at least 3-4 hours before or after entrectinib administration).

Medications that prolong QT/QTc interval should be avoided. Subjects that require medications that prolong QT/QTc interval should be monitored closely during treatment.

5.6.3 Prohibited Medications

Subjects are prohibited from receiving the following therapies during the Screening and Treatment Phase of this trial:

- Anti-cancer systemic chemotherapy or biological therapy not specified in this protocol
- Concomitant use of chemotherapy
- Investigational agents other than entrectinib or PAC-1
- Radiation therapy
- Herbal medications (e.g., St. John's Wort)

Subjects who, in the assessment by the investigator, require the use of any of the aforementioned treatments for clinical management, but not for progressive disease, should be removed from the trial and replaced.

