6.4 Protocol Therapy Discontinuation

In addition to discontinuation from therapy related to toxicities as outlined above, a subject will also be discontinued from protocol therapy and followed per protocol under the following circumstances outlined below. The reason for discontinuation of protocol therapy will be documented on the electronic case report form (eCRF)

- If there is evidence of disease progression
- If the treating physician thinks a change of therapy would be in the best interest of the subject
- If the subject requests to discontinue protocol therapy
- If the protocol therapy exhibits unacceptable toxicity
- If a female subject becomes pregnant
- If there is a ≥ 4 week delay between cycles due to a treatment related adverse event.
- Subjects can stop study participation at any time. However, if they decide to stop, subjects will continue to be followed as per Section 7 calendar

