12. STATISTICAL CONSIDERATIONS

12.1 Study Design

This is a single arm study.

Phase 1b: The primary objective of the Phase Ib dose escalation cohort study is to establish the MTD of PAC-1 in combination with entrectinib in subjects with metastatic uveal melanoma. A standard “3+3” design will be used to establish the MTD. PAC-1 (PO) will be given daily on Days 1 through 21 of each cycle. Entrectinib (PO) will be given daily on Days 1 through 28 of each cycle. Each cycle will equal 28 days. Response will be evaluated after every 2 cycles. Treatment will continue until disease progression based on RECIST criteria or intolerable toxicity.

Phase 2: The primary objective of the Phase II trial is to estimate 3 months PFS using RECIST v1.1 in subjects with metastatic uveal melanoma treated with PAC-1 in combination with entrectinib. PAC-1 (PO) will be given daily on Days 1 through 21 of each cycle. Entrectinib (PO) will be given daily on Days 1 through 28 of each cycle. Each cycle will equal 28 days. Response will be evaluated after every 2 cycles. Treatment will continue until disease progression based on RECIST criteria or intolerable toxicity. Subjects who voluntarily stop the study, have progressive disease, or unacceptable toxicities will be followed for survival every 2 months for 12 months from start of study treatment, then every 3 months for up to 24 months.

Correlative research analyses include examining the relationship between procaspase 3 expression in archived tumor tissue to degree of clinical response.

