12.3 Sample Size and Accrual

Previous studies in the target population identified PFS at 3 months of 38%.⁶ We hypothesize PFS at 3 months of 65%. Controlling for a probability of Type I error at 0.05 (one-sided), our sample size in Phase 2 is estimated to be 32 to ensure 90% statistical power in successfully detecting an alternative PFS rate at 3 months of 0.65, compared to a null rate of 0.38. With 3 additional patients to account for a 10% drop off rate, sample size for phase 2 study will be 35. Sample size analyses were conducted using the PASS software (NCSS, Kaysville, Utah, USA). With phase 1b study component, the study will need to have 3 subjects from Dose Level 1 of Phase 1b + 6 subjects from Dose Level 2 of Phase 1b (and carried over to Phase 2 study). The total number of subjects for the study is 38.

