12.4 Analysis Datasets

12.4.1 Evaluable for Safety

This will be comprised of all subjects who receive at least one dose of trial drug.

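### Section 5.6.3 lets dosed Phase 2 subjects be replaced for a post-baseline, investigator-judged reason, which can bias 3-month PFS upward

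*Combined protocol and SAP*

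**What the plan says.** Section 5.6.3 lists the prohibited therapies: other systemic anti-cancer or biological treatment, chemotherapy, other investigational agents, radiation and herbal products. On timing it says: "Subjects are prohibited from receiving the following therapies during the Screening and Treatment Phase of this trial". The consequence applies to "Subjects who, in the assessment by the investigator, require the use of any of the aforementioned treatments for clinical management", with an exception where the need arises from progressive disease. Such subjects "should be removed from the trial and replaced". The rule sets no cap and no time limit, and does not separate Phase 1b from Phase 2.

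Other sections bear on the same subjects:

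- Section 5.5 says that a clinical indication for a prohibited medication may mean stopping trial therapy. It does not mention leaving the trial or replacement.
- Section 6.4 says that, in the circumstances it lists, "a subject will also be discontinued from protocol therapy and followed per protocol". It adds that subjects who stop participating are still followed under the Section 7 calendar.
- Section 12.3 sets Phase 2 at 32, and then 35: "With 3 additional patients to account for a 10% drop off rate". The study total is 38. Section 12 does not mention replacement.
- Section 12.4.2, the only efficacy set defined, requires at least one cycle and a disease re-evaluation, or objective progression before Cycle 1 ends.
- Section 9.9.3 censors subjects without progression at their last disease evaluation.
- Section 7 footnote 6 places the first on-treatment scan before Cycle 3. After treatment stops, it records scans where available, until progression, death or another treatment.

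On design, Section 12.1 states: "This is a single arm study".

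**The concern.** The decision to remove and replace is made after dosing, by an investigator who knows the subject's course, and for a reason that may be linked to outcome. Take a subject who needs radiation for a symptomatic lesion before the first scan. No on-treatment RECIST assessment exists yet, and Section 9.8 keeps symptomatic deterioration separate from objective progression. Whether the need counts as being for progressive disease is then a judgement, and one answer takes the subject out and brings in a new one.

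Nothing later in the plan clearly puts that subject back into the primary analysis. Someone removed before the first scan would normally fall outside the Section 12.4.2 set. With no control arm subject to the same rule, selective loss of poor-prognosis subjects raises the observed 3-month PFS rate against a fixed 38%. OS could be affected in the same way.

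**Working it through.** **Inputs.** From Section 12.3: null rate p0 = 0.38, alternative p1 = 0.65, one-sided alpha 0.05, power 90%, n = 32, and 35 after drop-off. The documents give no success cut-off and no replacement rate, so both are assumptions below. The test is taken as an exact one-sample binomial.

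**Reproducing the plan's sample size.** At n = 32 the smallest cut-off with P(X ≥ r | 0.38) ≤ 0.05 is r = 18, with exact error 0.0275 and power 0.888. Exact power is 0.923 at n = 33, and the continuity-corrected normal formula gives 31. So 32 is reproduced to within one or two subjects and is not in dispute. Drop-off: 32 + 3 = 35. Study total: 3 (Dose Level 1) + 35 = 38, which leaves nothing for replacements.

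**Reference rule at n = 35.** The smallest cut-off is 19: P(X ≥ 19 | 0.38) = 0.0367, power 0.932.

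**Worst case, by fraction replaced.** Let q be the fraction of all treated subjects who are removed, every one a would-be failure, with enrolment continuing until n are retained. The success rate among retained subjects is p* = 0.38/(1 − q), and the expected number of replacements at n = 35 is 35q/(1 − q).

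| q | p* | Expected replacements (n = 35) | Error, n = 35, cut-off 19 | Error, n = 32, cut-off 18 |
|---|---|---|---|---|
| 0 | 0.380 | 0 | 0.0367 | 0.0275 |
| 0.05 | 0.38/0.95 = 0.400 | 1.84 | 0.0615 | 0.0463 |
| 0.10 | 0.38/0.90 = 0.422 | 3.89 | 0.102 | 0.0775 |
| 0.15 | 0.38/0.85 = 0.447 | 6.18 | 0.166 | 0.128 |

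Here q is a fraction of all subjects, not of failures.

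**Worst case, by fixed count.** If k failures are each replaced by a new subject with success rate 0.38 and the cut-off stays at 19, the error is P(X ≥ 19) with X binomial(35 + k, 0.38). This is 0.051, 0.068 and 0.089 for k = 1, 2 and 3. At n = 35 one such replacement just passes 0.05. At n = 32 it takes two (0.039, then 0.055).

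**Less extreme cases.** If removed subjects would have succeeded at rate s, then p* = (0.38 − s·q)/(1 − q). With s = 0.38, p* = 0.38 for any q, so there is no bias. With s = 0.19 and q = 0.10, p* = (0.38 − 0.019)/0.90 = 0.401, about the same as the 5% row.

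**Cost of keeping these subjects as failures.** With 35 in the denominator and k of them counted as failures, power is P(X ≥ 19) with X binomial(35 − k, 0.65). This is 0.932, 0.901, 0.859 and 0.804 for k = 0, 1, 2 and 3. The error falls to 0.0258, 0.0176 and 0.0115 for k = 1, 2 and 3.

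**The case against.** The strongest case against is that the rule already excludes need arising from progressive disease, and that it never offers death as a reason to replace anyone. A reader might infer that recorded endpoint failures can be swapped out. The text does not support that. The exception is also not worded as RECIST progression, so an investigator could treat a growing symptomatic lesion as falling under it. Herbal use is a trigger too and need not predict outcome. This stands, and it limits the concern to likely or not-yet-documented failures.

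A reader might also infer that removal ends PFS and OS collection. Section 5.6.3 says nothing about data or follow-up. Section 5.5 speaks only of stopping trial therapy, Section 6.4 continues follow-up, and Section 7 footnote 13 provides for survival follow-up. So loss of data is an inference from the wording about removal and replacement, not something stated.

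Nor does Section 12.4.1 conflict with the rule. Its safety set is described as "This will be comprised of all subjects who receive at least one dose of trial drug", which holds whether or not a subject is later replaced. A drop-off allowance and a replacement rule overlap without contradicting each other, and Section 12.3.1 calls 35 a projected figure.

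Finally, Section 12.5.1 plans Kaplan-Meier curves and median PFS and names no binomial test, so the error rates above are illustrative. That stands as well, but the direction of the bias does not depend on the test.

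**Conclusion.** The concern holds in a limited form. Section 5.6.3 is an operative, uncapped instruction that lets dosed Phase 2 subjects be exchanged for a post-baseline reason judged without blinding, and no other section says how they count in 3-month PFS. It is in tension with Sections 5.5 and 6.4 on what removal means, overlaps with the three subjects added in Section 12.3, and has no provision in the total of 38.

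The error rates of 0.062, 0.102 and 0.166 are worst-case values. They rest on n = 35, an assumed cut-off of 19, replacement of 5%, 10% or 15% of all subjects, and every replaced subject being a certain failure. They should not be read as expected inflation. The replacement rate is unknown, and the bias is zero if replaced subjects have average prognosis. This should be fixed because the primary endpoint is exposed and the correction is cheap, but the documents do not show that the result would be invalidated.

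**What to change.** In Section 5.6.3, state that Phase 2 subjects who have received study drug are not replaced, remain in the primary 3-month PFS and OS analyses, and continue to be followed for progression and survival. Limit any replacement to subjects who never received study drug.

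Changing that sentence alone is not enough, because other rules can drop or censor the same subjects. Align Sections 12.4.2 and 9.9.3 and Section 7 footnote 6 so that these subjects are in the 3-month PFS denominator. Those without a documented progression-free status at 3 months should count as not progression-free, at least in a sensitivity analysis.

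Reconcile Sections 5.5, 5.6.3 and 6.4 on what removal from the trial means for follow-up and counting. Which therapies are allowed, and whether study drug stops, are clinical matters on which this point takes no position.

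The cost is a short amendment across these sections and possibly some off-treatment scans, since footnote 6 now records them only where available and footnote 13 leaves later imaging to the physician. The observed rate may be slightly less favourable. Power falls from 0.932 to 0.901, 0.859 or 0.804 if one, two or three such subjects count as failures.
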